9.7.2 Determination of Sample Size

The sample size is estimated based on the primary endpoint of PFS. Approximately 1050 subjects will be randomized in a 1:1:1 ratio into 1 of 3 treatment arms: lenvatinib + everolimus, lenvatinib + pembrolizumab, or sunitinib alone. The randomization scheme will be stratified by geographic region (Western Europe + North America vs. Other) and MSKCC prognostic groups (favorable, intermediate and poor risk).

The same treatment effect is assumed for the primary comparisons of lenvatinib + everolimus (Arm A) and lenvatinib + pembrolizumab (Arm B) each compared to sunitinib alone (Arm C). Assuming the median PFS of sunitinib to be 12.3 months and a targeted HR of 0.714 for the primary comparisons, this corresponds to a 40% improvement (4.9 months) in median PFS from 12.3 months to 17.2 months for Arm A versus Arm C and for Arm B versus Arm C. A yearly loss of PFS event rate of 22% is assumed in the sample size calculation.

Since the study is testing more than one comparison for the primary and secondary endpoints, the graphical approach ([Section 9.7.4](#)) will be used for testing multiple hypotheses. For the two PFS comparisons (one for each test arm), the sponsor chooses to split the total alpha of 0.0499 (2-sided), as initial allocations, into $\alpha = 0.045$ for the comparison between Arm B and Arm C, and $\alpha = 0.0049$ for the comparison between Arm A and Arm C.

The study is designed to achieve 90% power at $\alpha = 0.045$ to detect a statistically significant difference in PFS in the comparison between Arm B and Arm C. Therefore, a total of 388 PFS events are required between Arms B and C in the final PFS analysis. Since the same number of PFS events are expected to be observed in Arms A and C, a total of 388 PFS

events is expected in the final PFS analysis for the comparison between Arms A and C. The power to detect a statistically significant difference in PFS between Arm A and Arm C is approximately 70% at the initial assigned $\alpha = 0.0049$, and will be at least 90% when the hypothesis tests of PFS and OS in the comparison of Arm B and Arm C are statistically significant, and vice versa. In the power calculation for PFS analysis, it is assumed that one interim analysis of PFS is to be performed at the 80% information fraction and a Lan-DeMets spending function with O'Brien-Fleming boundary is used between the interim and final analysis of PFS.

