## 4 DETERMINATION OF SAMPLE SIZE

The sample size is estimated based on the primary endpoint PFS. Approximately 1050 subjects will be randomized in a 1:1:1 ratio into one of the three treatment arms: lenvatinib + everolimus, lenvatinib + pembrolizumab, or sunitinib alone. The randomization scheme will be stratified by geographic region (Western Europe and North America versus Other) and MSKCC prognostic groups (favorable, intermediate and poor risk).

The same treatment effect is assumed for the primary comparisons of lenvatinib + everolimus (Arm A) and lenvatinib + pembrolizumab (Arm B) each compared to sunitinib alone (Arm C). Assuming the median PFS in sunitinib alone (Arm C) to be 12.3 months and a hazard ratio of 0.714 for the primary comparisons, this corresponds to 40% improvement (4.9 months) in median PFS from 12.3 months to 17.2 months for Arm A versus Arm C and for Arm B versus Arm C. A yearly loss of PFS event rate of 22% is assumed in the sample size calculation. Since the study is testing more than one comparison for the primary and secondary endpoints, the graphical approach (SAP [Section 5.3.3](#)) will be used for testing multiple hypotheses. For the two PFS comparisons (one for each test arm), the sponsor chooses to split the total alpha of 0.0499 (2-sided), as initial allocations, into  $\alpha = 0.045$  for the comparison between Arm B and Arm C, and  $\alpha = 0.0049$  for the comparison between Arm A and Arm C.

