## 5.2 Study Subjects

### 5.2.1 Definitions of Analysis Sets

The following analysis sets will be defined:

- The Full Analysis Set (Intent-to-Treat Analysis [ITT] Population) is the group of all randomized subjects regardless of the treatment actually received. This is the primary analysis population used for all efficacy analyses which will be based on the intent-to-treat principle.
- The Per Protocol Analysis Set is the subjects who received at least one dose of

any study drug, had no major protocol deviations and had both baseline and at least 1 postbaseline tumor assessments. Subjects who died prior to the first postbaseline tumor assessment will also be included. The per protocol analysis set will be the secondary analysis set for efficacy endpoints.

- The Safety Analysis Set is the group of subjects who received at least one dose of any study drug. This is the analysis population for all safety analyses, which will be based on as-treated principle.
- Population Pharmacokinetic (PK) Analysis Set: All subjects who have received at least one dose of study treatment with documented dosing history in the lenvatinib plus everolimus arm (Arm A) or the lenvatinib plus pembrolizumab arm (Arm B), and have measurable plasma levels of lenvatinib or whole blood levels of everolimus.

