#### 5.4.2 Secondary Efficacy Analyses

All analyses of secondary efficacy endpoints will be performed based on Full Analysis Set as the primary analysis set and Per Protocol analysis set as the secondary analysis set.

1. Overall Survival (OS) will be compared between lenvatinib + everolimus (Arm A) and sunitinib alone (Arm C), and between lenvatinib + pembrolizumab (Arm B) and sunitinib alone (Arm C), using the stratified log-rank test with geographic region and MSKCC prognostic groups as strata. The hazard ratio and its 95% CI comparing lenvatinib + everolimus (Arm A) versus sunitinib alone (Arm C) and lenvatinib + pembrolizumab (Arm B) versus sunitinib alone (Arm C) will be estimated by a stratified Cox proportional hazards model with Efron's method for ties, stratified by geographic region and MSKCC prognostic groups. Median OS

and the OS rate at 12, 18, 24 months, and so on (depending on data adequacy) with 2-sided 95% CIs will be calculated using K-M product-limit estimates for each treatment arm and K-M estimates of OS will be plotted over time. Three interim and a final analyses of OS are planned to be performed (SAP [Section 6](#)). Lan-DeMets spending function with Pocock boundary will be used to control alpha levels among the interim and final analysis of OS (SAP [Section 5.3.3](#)). The first two OS interim analyses will be performed at the time of PFS interim and final analysis, corresponding to approximately 45% and 60% of information fractions of OS events. The third OS interim analysis will be performed at approximately 80% information fraction of OS events. The final analysis of OS will be performed when 304 OS events are observed for each comparison.

All events of death will be included, regardless of whether the event occurred while the subject was still taking study drug, or after the subject discontinued study drug. Subjects who were alive at the data cutoff date will be censored at the data cutoff date. Subjects who were lost to follow-up or withdrew consent will be censored at the date the subject was last known to be alive.

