2. Objective Response Rate (ORR), estimated by treatment arms based on the tumor response evaluation by IIR according to RECIST 1.1, will be calculated with exact 95% confidence intervals using the method of Clopper and Pearson. The difference between treatment arms comparing lenvatinib + everolimus (Arm A) versus sunitinib alone (Arm C) and lenvatinib + pembrolizumab (Arm B) versus sunitinib alone (Arm C) will be tested using the Cochran-Mantel-Haenszel (CMH) test, stratified by geographic region and MSKCC prognostic groups. The 2-sided 95% CIs for the odds ratio and the difference in ORR will be calculated. The p-value for hypothesis testing of ORR will be based on the ORR data at the time of the PFS interim analysis. The ORR data available at the subsequent analysis time points will be provided for supportive purposes.

For the adjustment of multiplicity of primary endpoint PFS, key secondary endpoints ORR and OS, please refer to SAP [Section 5.3.3](#). There is no multiplicity adjustment to be made for other secondary and exploratory efficacy endpoints. For statistical tests to be performed on other secondary and exploratory efficacy endpoints, nominal p-values will be generated.

PFS2 will be evaluated using K-M estimates and difference in PFS2 will be tested by stratified log-rank test, stratified by geographic region and MSKCC prognostic groups. The hazard ratio (lenvatinib + everolimus relative to sunitinib and lenvatinib + pembrolizumab relative to sunitinib) and the corresponding 95% confidence intervals (CIs) will be estimated using the Cox regression model with Efron's method for ties, stratified by the same stratification factors. Patients alive and for whom a disease progression on second line therapy has not been observed will be censored at the last time known to be alive. Subjects who did not have second line therapy and no death documented before data cutoff date will be censored at the data cutoff date. Time to next-line therapy will be summarized only for subjects who experience the next-line therapy. It is defined as the time between

randomization and the start date of next-line therapy. The median and quantile of time to initiation of next-line therapy will be summarized.

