Dose reduction could be applied to lenvatinib (either 20mg/day or 18mg/day reduce to 14, 10, and 8 mg/day), everolimus (5 mg every day reduce to 5 mg every other day), and sunitinib (50 mg/day reduce to 37.5, 25 mg/day of schedule 4/2). Dose interruption could apply to all study drugs. Definition of dose interruption only includes the scenario that the before and after dose 0 (interruption period), the dose levels or dosing frequency are the same. For example: 20 mg lenvatinib followed by 0 mg and followed by 20 mg lenvatinib; 5 mg everolimus every day followed by 0 mg followed by 5 mg everolimus every day. If dose level reduces from previous dose level after dose interruption period (dose 0), it should count into dose reduction not dose interruption. For example: (1) 20 mg/day lenvatinib followed by 0 mg followed by 14 mg/day lenvatinib; (2) 5 mg everolimus every day followed by 0 mg followed by 5 mg everolimus every other day; the period with 0 mg should not count into dose interruption instead should count as dose reduction. If after dose 0 mg, the subject discontinued from treatment permanently, it should count as treatment discontinuation instead of dose interruption.

Number of subjects with dose reductions and dose interruptions of lenvatinib, everolimus, sunitinib, and pembrolizumab (dose reduction not applied to pembrolizumab) will be summarized by frequency counts and percentages according to study medication data.

Time to first dose reduction is defined as the date of the first dose to the date of first dose reduction, or the date of first dose interruption if subjects had dose interruption followed by dose reduction. There will be two ways to estimate the time to dose reduction. (1) Only include the subjects who had dose reduction events. Descriptive statistics will be generated to describe the time to first dose reduction for these patients. (2) Include all subjects. For subjects who did not have dose reduction, it will be censored at the date of last dose. For this summary, Kaplan-Meier method will be used to estimate the median time to first dose reduction for all the subjects by the treatment arms.

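### Time to next-line therapy is summarized only in subjects who started it (SAP 5.4.2), so at the month-38 and month-45 cutoffs the medians are too short and hide most of any delay; the summary is descriptive, and an all-randomized estimate should be added

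*SAP*

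**What the plan says.** SAP Section 5.4.2 introduces time to next-line therapy at the end of the PFS2 paragraph. It runs from randomization to the start of next-line therapy. The population is restricted: "Time to next-line therapy will be summarized only for subjects who experience the next-line therapy". The output is "The median and quantile of time to initiation of next-line therapy will be summarized". No censoring rule, Kaplan-Meier curve, cumulative incidence, confidence interval or test is given for it, and no version in all randomized subjects appears elsewhere in the SAP.

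Three neighbouring provisions help in reading it:

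- PFS2, in the same paragraph, is analysed in all subjects by Kaplan-Meier, stratified log-rank and stratified Cox. Living subjects without second-line therapy are censored rather than dropped.
- For time to first dose reduction, SAP Section 5.6.1.3 gives an events-only summary and, beside it, a censored all-subject version: "Kaplan-Meier method will be used to estimate the median time to first dose reduction for all the subjects by the treatment arms".
- Time to next-line therapy is not among the endpoints in SAP Section 5.1 or Protocol Section 9.7.1.1.

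**The concern.** Starting next-line therapy happens after randomization, and a regimen that works longer makes it rarer by any given date. Keeping only subjects in whom it has happened selects on the outcome and cuts every time off at the data cutoff. Subjects not yet switched, who have the longest times, are removed, and more of them come from the better arm. Subjects who died or were lost before switching go too.

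The resulting median answers when switched subjects were switched. It does not answer how long a regimen puts off the next therapy. A reader who sees medians counted from randomization, arm beside arm, will probably take them for the second quantity. The medians also lengthen as follow-up lengthens, so interim and final values cannot be compared.

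**Working it through.** **Inputs.** From SAP Section 4: "Assuming the median PFS in sunitinib alone (Arm C) to be 12.3 months and a hazard ratio of 0.714 for the primary comparisons", described as a "40% improvement (4.9 months) in median PFS from 12.3 months to 17.2 months"; a 34-month enrollment period; PFS cutoffs near months 38 and 45; final OS near month 69; yearly loss of 3% (OS) and 22% (PFS).

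**Assumption.** The documents give no time-to-next-line distribution. The planned PFS medians stand in for it, with exponential times and uniform accrual.

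**1. The plan's own figure.** Freedman's formula with two-sided alpha 0.045, 90% power and HR 0.714:

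(1.714/0.286)² × (2.005 + 1.282)² = 35.92 × 10.80 ≈ 388 events, as stated. Schoenfeld's formula gives 381.

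Under the same accrual model with 22% yearly loss, month 45 yields 580 events in three arms (stated 582) and 399 in two arms (stated 388). The model therefore reproduces the sponsor's timeline.

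**2. Median among starters.** With hazard λ = ln 2 / median and loss hazard c, observed start times at cutoff T have density proportional to

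λ·exp(−(λ + c)t)·G(t), where G(t) = 1 for t ≤ T − 34 and (T − t)/34 thereafter.

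The starters-only median is the median of that density. The true difference is 17.2 − 12.3 = 4.9 months.

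| Cutoff (month) | Yearly loss | Started, C vs test | Starters-only medians | Difference | Share of 4.9 hidden |
|---|---|---|---|---|---|
| 38 | 0% | 64% vs 54% | 7.05 vs 8.00 | 0.95 | 81% |
| 38 | 3% | 63% vs 52% | 6.9 vs 7.8 | 0.9 | 81% |
| 45 | 0% | 76% vs 65% | 8.49 vs 9.76 | 1.27 | 74% |
| 45 | 3% | 74% vs 63% | 8.3 vs 9.5 | 1.2 | 75% |
| 69 | 0% | 94% vs 87% | 11.2 vs 14.1 | 2.9 | 41% |
| 69 | 3% | 90% vs 83% | 10.9 vs 13.6 | 2.7 | 44% |

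Between months 38 and 45 the Arm C median rises by about 1.4 months (7.05 to 8.49) from longer follow-up alone.

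**3. Range.** The inputs were varied: control medians of 12.3 to 24 months, true ratios of 1.4 or 2.0, yearly loss of 3% or 22%, and 3% loss with or without deaths before next-line therapy at 0.01 per month. The share hidden was 81-95% at month 38 and 75-93% at month 45.

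**4. All randomized subjects, non-starters censored.** Simulated Kaplan-Meier medians (350 per arm, 3% yearly loss) were 12.3 vs 17.3 at month 38 and 12.3 vs 17.2 at month 45, so the delay is recovered.

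**5. Against the estimator recommended below.** Cumulative incidence with death competing is a different quantity. With death hazard d = 0.01 per month, its median is −ln(1 − 0.5(λ + d)/λ)/(λ + d):

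- λ = 0.0564 gives 13.4 months.
- λ = 0.0403 gives 19.5 months.

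That is a difference of about 6.1. With the same deaths and 3% loss (replace c by c + d in step 2), starters-only medians are 6.4 vs 7.2 at month 38 and 7.65 vs 8.75 at month 45, differences of 0.8 and 1.1. The 75-80% in step 2 is thus measured against a censored Kaplan-Meier median; against cumulative incidence the shortfall is no smaller.

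**The case against.** The case for leaving the sentence alone is substantial.

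- **Role.** The variable supports no objective, is on no endpoint list and has no test, interval or hazard ratio. The SAP does not say that it measures how long a regimen delays the next therapy, and the sentence states its own population. Nor does it say that the medians will be shown by arm, although that is the likely layout. All of this stands and caps the severity.
- **Coverage elsewhere.** PFS by independent review, PFS by investigator and PFS2 use all randomized subjects with censoring. This stands.
- **Direction.** Under the assumptions used, the rule shrinks differences, so it cannot create an apparent benefit for either combination. This stands.
- **Proxy.** PFS events include deaths, after which no next-line therapy starts, and treatment may continue past progression. The exact figures are therefore illustrative, though the range in step 3 leaves the conclusion at months 38 and 45 unchanged.
- **Convention.** Time to treatment failure due to toxicity and time to onset of events of clinical interest are also summarized only in affected subjects. That is fair, but consistency does not make the medians interpretable as delay. Median duration of response among responders is a weaker parallel: response starts that clock, whereas here the restriction is on the event that ends it.

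A reader might infer that the SAP breaks its own intent-to-treat rule. The documents do not clearly support that. The sentence in Section 5.4.2, "All analyses of secondary efficacy endpoints will be performed based on Full Analysis Set as the primary analysis set", covers secondary efficacy endpoints, and this variable is not one. Section 5.2.1 is broader ("This is the primary analysis population used for all efficacy analyses which will be based on the intent-to-treat principle"), but the SAP summarizes subsets elsewhere, so the mismatch is one of spirit.

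**Conclusion.** The point holds as a minor one. Followed as written, SAP Section 5.4.2 gives medians that are too short, that depend on the cutoff, and that hide roughly 75-80% of a 4.9-month delay at the two PFS cutoffs. This rests on next-line timing following the planned PFS medians, exponential times, uniform 34-month accrual and 0-3% yearly loss.

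Two stronger readings should be resisted:

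- Most of the delay is not hidden at every cutoff. At month 69, with 0-3% loss and no competing deaths, 41-44% is. That date falls after the randomization phase, which is this SAP's scope; Section 5.9 leaves extension-phase analyses to a separate SAP if needed.
- The rule does not threaten the trial's conclusions. It affects no alpha, boundary or claim.

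**What to change.** Add to SAP Section 5.4.2 an estimate by treatment arm in the Full Analysis Set:

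- Event: start of next-line anticancer therapy, timed from randomization.
- Competing event: death before next-line therapy.
- Censoring: subjects with neither event, at the last contact with subsequent-therapy status recorded, or at data cutoff if earlier.
- Output: cumulative incidence curves, the median if reached, rates at 6, 12, 18 and 24 months with 95% CIs, and the percentage starting in each arm.

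If the starters-only medians are kept, label them as describing switched subjects only and not for between-arm comparison. This follows the two-version pattern the SAP already uses for time to first dose reduction.

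The cost is a short passage of SAP text and one standard table and figure. No new data are needed: survival and subsequent anticancer treatments are followed every 12 weeks (Protocol Section 9.1.2.2), and anticancer therapy is recorded until death or the end of survival follow-up (Protocol Table 7 footnotes). One small downside is that the better arm's median may not be reached at the first cutoff, which is why fixed-time rates are included.

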### 5.4.3 Other Efficacy Analyses

All statistical tests specified in this section will be performed for exploratory purpose and no multiplicity adjustment will be made.

#### 5.4.3.1 Other Analyses of Tumor Response Using RECIST 1.1

The best overall response categories (CR, PR, SD [including non-CR/non-PD], durable SD (duration of SD  $\geq$  23 weeks), PD, NE, Unknown) will be derived based upon time point tumor responses during the study as assessed by IIR as well as the Investigator. BOR of SD must occur at least 49 days after randomization. If a subject has a BOR of non-CR/non-PD, the subject's BOR will be grouped with the SD category.

The counts/percentages will be calculated for each BOR category by treatment group. Concordance and discordance on BOR for each subject between assessment by IIR and by investigator review will be analyzed. Also, Cohen's kappa statistic will assess the overall concordance for each treatment group (Fleiss et al., 2003).

Median duration of response among responders for each treatment arm will be presented along with its corresponding 2-sided 95% CIs. Censoring rules for DOR are the same as those of PFS (Table 4).

Disease Control Rate (DCR) and Clinical Benefit Rate (CBR) will be calculated with exact 95% confidence intervals using the method of Clopper and Pearson. The differences and odds ratios of the above rates between treatment arms and corresponding two-sided 95% CIs will be calculated respectively. These analyses will be performed based on both IIR and investigator assessments. The null hypothesis of no difference in DCR and CBR comparing lenvatinib + everolimus (Arm A) versus sunitinib alone (Arm C) and lenvatinib + pembrolizumab (Arm B) versus sunitinib alone (Arm C) will be tested using the CMH test stratified by geographic region and MSKCC prognostic groups.

The difference in PFS between lenvatinib in combination with everolimus (Arm A) versus lenvatinib in combination with pembrolizumab (Arm B) will be tested by stratified log-rank test, stratified by geographic region and MSKCC prognostic groups. The hazard ratio and the corresponding 95% CI will be estimated using the Cox regression model with Efron's method for ties, stratified by the same stratification factors. The difference in OS between lenvatinib in combination with everolimus (Arm A) versus lenvatinib in combination with pembrolizumab (Arm B) will be analyzed similarly.

Exploratory analyses may also be conducted using IMDC risk category and geographic region as the stratification factors for the endpoints PFS and OS.

An analysis of overall concordance on PFS for each treatment group between assessment by IIR and by investigator review will be performed.

In addition, exploratory analyses may be conducted to include geographic region, MSKCC prognostic groups and other subgroups as covariates, respectively, for the endpoints PFS, OS, and PFS2.

## **5.5 Pharmacokinetic, Pharmacodynamic, Pharmacogenomic, and Other Biomarker Analyses**

PK sampling was to be performed for all subjects of serum lenvatinib (Arms A and B), and whole blood everolimus (Arm A). Details of the analysis methods for population PK/PD modeling will not be described in this SAP but will be described in a separate analysis plan.

